### 5.1.4 Visit Procedures

#### Visit 0: Inclusion, Allocation of Subject's number, Blood Sample (*For the Russian Federation only*)

- 1) Give the subject's parent(s) information about the trial, answer any questions, obtain written informed consent in duplicate (in 2 originals) and give him / her 1 signed original as per local regulations and practice.
- 2) Check inclusion and exclusion criteria for eligibility.
- 3) Collect demographic data.
- 4) Obtain medical history about the subject.
- 5) Perform a physical examination, including but not limited to examination of the head (including ear, nose, and throat), neck, thorax (including heart and lungs), abdomen, and extremities. If a routine examination, including examination by a neurologist, CBC, biochemistry, and urinalysis laboratory tests, had been performed within the last 7 days before Visit 0 by the Investigator, a sub-Investigator, or a licensed practitioner; it does not need to be repeated unless the Investigator considers it is necessary to repeat.
- 6) Perform a neurological examination by a neurologista
- 7) Take the subject's temperature by the axillary route.
- 8) Connect to the Interactive Web Response System (IWRS) for allocation of subject identification number
- 9) Obtain the first 7-mL blood sampleb (see [Section 7](#) for detailed instructions regarding the handling of blood samples). If attempts to obtain the first blood draw are unsuccessful (after reasonable attempts as per local regulations / practice), then Visit 0 can be rescheduled to a later date at which point inclusion/exclusion criteria must be re-validated. If the first blood draw cannot be obtained, the subject will be withdrawn from the study without being vaccinated.
- 10) Obtain a urine sample (approximately 8 mL)c
- 11) Collect reportable concomitant medications information
- 12) Complete relevant source documentation and CRF pages for the visit
- 13) Confirm subject's eligibility based on the results of the baseline testing of CBC, blood chemistry, and urinalysis, and neurological examination.

a The results (discharge summary) of the neurologist's examination, performed for the subject in terms of routine practice, can be used, if the examination was done within 7 days before Visit 0.

b The results of CBC and biochemistry laboratory tests, performed for the subject in terms of routine practice, can be used, if the tests were done within 7 days before Visit 0. In this case, the blood sample volume collected at Visit 0 will be 5 mL.

c The results of urine laboratory tests, performed for the subject in terms of routine practice, can be used if the tests were done within 7 days before Visit 0. In this case, no urine sample will be collected at Visit 0.

**Note:** If Visit 1 (the vaccination visit) is performed on the same day as Visit 0, only the procedures from step number 4 onwards in the Study Procedures listed under Visit 1 below are to be followed.

**Visit 1 (D0): Randomization and Vaccination (*For the Russian Federation only*)**

*Steps 1 through 3 only for subjects with Visit 0 and Visit 1 not on the same day:*

- 1) Check inclusion and exclusion criteria for eligibility
- 2) Perform a physical examination
- 3) Take the subject's temperature by the axillary route.

*Steps 4 through 10 for all subjects:*

- 4) Connect to the Interactive Web Response System (IWRS) for subject randomization and obtain group of vaccination allocated.
- 5) Inject the appropriate study vaccine(s). For Group 7, MenACYW conjugate vaccine should be given first. Each vaccine should be given in an assigned location (either the right or left respective limb) and documented appropriately.

**MenACYW conjugate vaccine (Groups 7 and 8):** Inject IM into the anterolateral area of the thigh or the deltoid muscle of the arm.

**PCV13 vaccine (Groups 7 and 9, the Russian Federation only):** Inject IM into the anterolateral area of the thigh or the deltoid muscle of the arm.

- 6) Keep the subject under observation for 30 minutes, and record any AE in the source document.
- 7) Give the parent a diary card, a thermometer, and a ruler, and go over the instructions for their use.
- 8) Remind the parent to expect a telephone call 8 days (+2 days) after Visit 1 and to bring back the diary card when they return for Visit 2 at a specified date and time.
- 9) Remind the parent to notify the site in case of an SAE.
- 10) Complete the relevant CRF pages for this visit.

**Visit 1 (D0): Inclusion, Randomization, Blood Sample, and Vaccination (*for South Korea, Mexico, and Thailand*)**

- 1) Give the subject's parent(s) / guardian information about the trial, answer any questions, obtain written informed consent in duplicate (in 2 originals, or a photocopy of the signed consent) and give him / her 1 signed original or the copy as per local regulations and practice.
- 2) Check inclusion and exclusion criteria for eligibility.
- 3) Collect demographic data.
- 4) Obtain verbal medical history about the subject.

- 5) Perform a physical examination, including but not limited to examination of the head (including ear, nose, and throat), neck, thorax (including heart and lungs), abdomen, and extremities. If a routine examination had been performed within the last month by the investigator, a sub-investigator, or a licensed nurse practitioner, it does not need to be repeated unless there were some changes in health status, in which case it may be limited to the affected area.
- 6) Take the subject's temperature by either the rectal or axillary route.
- 7) Connect to the Interactive Web Response System (IWRS) for subject identification number and randomization.
- 8) Obtain the first 5-mL blood sample (see [Section 7](#) for detailed instructions regarding the handling of blood samples). If attempts to obtain the first blood draw are unsuccessful (after reasonable attempts as per local regulations / practice), then Visit 1 can be rescheduled to a later date at which point informed consent and inclusion/exclusion criteria must be re-validated. If the first blood draw cannot be obtained, the subject will be withdrawn from the study without being vaccinated.
- 9) Inject the appropriate study vaccine(s). Of the injected vaccines, MenACYW conjugate vaccine should be given first. Each vaccine should be given in an assigned location (either the right or left respective limb) and documented appropriately.  
**For South Korea and Thailand only**, the order of the remaining vaccines is not critical, as long as each is given in an assigned location and documented appropriately. To avoid confusion, staff should follow normal office procedure for order of vaccine administration. If injections are given in the same limb, the injection sites should be at least 2.5 cm (1 inch) apart. If injection(s) and blood sampling are done in the same limb, the injection site(s) and blood sampling site should be at least 2.5 cm (1 inch) apart or can be done according to local clinical practice as per the Investigator's judgment.

**MenACYW conjugate vaccine (Groups 1, 2, 4, 5, 10, and 11):** Inject IM into the anterolateral area of the thigh or the deltoid muscle of the arm.

**MMR vaccine and V vaccine (Groups 1, 3, 10, and 12; South Korea and Thailand only):** Inject SC into the fatty tissue over the triceps on the upper arm or fatty tissue over the anterolateral thigh muscle

**DTaP-IPV-HB-Hib vaccine (Groups 4 and 6, Mexico only):** Inject IM into the anterolateral area of the thigh or the deltoid muscle of the arm.

- 10) Keep the subject under observation for 30 minutes, and record any AE in the source document.
- 11) Give the parent / guardian a diary card, a thermometer, and a ruler, and go over the instructions for their use.
- 12) Remind the parent / guardian to expect a telephone call 8 days (+2 days) after Visit 1 and to bring back the diary card when they return for Visit 2 at a specified date and time.
- 13) Remind the parent / guardian to notify the site in case of an SAE.
- 14) Complete the relevant CRF pages for this visit.

Telephone Call 1 (8 days [+2 days] after Visit 1)

**Note:** If D08 falls on a weekend or a holiday, the telephone call may be made on the following business day.

- 1) Record relevant information concerning the subject's health status on the telephone contact form. If an SAE occurred, follow the instructions in [Section 10](#) for reporting it.
- 2) Remind the parent / guardian to do the following:
  - Complete the D0 to D07 pages of the diary card.
  - Complete the remaining pages of the diary card, and bring them to Visit 2.
  - Notify the site in case of an SAE.
  - Confirm the date for the next visit

Visit 2 (30 days [+14 days] after Visit 1): Collection of Safety Information and Blood Sample

- 1) Review the pages of the diary card with the parent / guardian, including any AEs, medications, or therapy that occurred since vaccination. The parent / guardian must return the diary card.
- 2) Review the temporary contraindications for Visit 2 blood draw (see [Section 5.2.8](#)).
- 3) **For subjects enrolled at sites in the Russian Federation only:** Obtain the second 7-mL blood sample (for CBC, blood chemistry, and immunogenicity assessment) and urine sample for urinalysis. Perform a neurological examination by a neurologist.
- 4) **For subjects enrolled at sites in South Korea, Mexico, and Thailand only:** Obtain the second 5-mL blood sample (see [Section 7.1](#) for detailed instructions regarding the handling of blood samples).
- 5) Complete the termination record of the CRF
- 6) If the subject's parent / guardian does not return for Visit 2, and the diary card is not received at the site, site personnel will contact the subject's parent / guardian by telephone. During the telephone call, the subject's parent / guardian will be reminded to return the diary card to the study site. Telephone calls will be documented on the Telephone / Interview Record. If the study personnel are unable to contact the subject's parent / guardian with 3 attempts, the study personnel will follow instructions given in [Section 5.2.10](#).

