#### **5.2.9 Conditions for Withdrawal**

Parents / guardians will be informed that they have the right to withdraw their child from the trial at any time. A subject may be withdrawn from the study:

- At the discretion of the Investigator or Sponsor due to safety concerns (withdrawal) without the subject's permission
- At the request of the subject's parent / guardian (dropout)

The following will result in automatic withdrawal or exclusion of a subject from the study:

- Significant non-compliance with the protocol, based on the Investigator's judgment

The reason for a withdrawal or dropout should be clearly documented in the source documents and on the CRF.

The Investigator must determine whether voluntary withdrawal is due to safety concerns (in which case, the reason for discontinuation will be noted as "SAE" or "other AE" as appropriate) or for another reason.

Withdrawn subjects will not be replaced.

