### 6.4 Blinding and Code-breaking Procedures

This trial is open label; therefore, there is no need for code-breaking procedures.

Until database lock and to prevent biases, the laboratory personnel performing the serology testing will be blinded to the group assignment. The laboratory will have a written procedure detailing how the blinding will be maintained.

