### 6.5 Randomization and Allocation Procedures

**For sites in South Korea, Mexico, and Thailand:** Each 12- to 23-month old subject whose parent(s) / guardian signs the ICF, and who meets the inclusion/exclusion criteria will be randomly assigned in a 2:1:1 ratio to the study groups by country.

**For sites in the Russian Federation:** Each toddler aged 12 to 14 months or 16 to 23 months on the day of enrollment will be assigned to Group 8 with a balanced population distribution of half of the subjects aged 12 to 14 months and half of the subjects aged 16 to 23 months. Those aged 15 to 23 months on the day of enrollment will be randomized in a 2:1 ratio to Groups 7 and 9.

**Site staff will connect to the IWRS, enter identification and security information, and confirm a minimal amount of data in response to IWRS prompts.** The IWRS will then provide the group assignment and have the site staff confirm it. The full detailed procedures for group allocation are described in the Operating Guidelines. If the subject is not eligible to participate in the trial, then the information will only be recorded on the subject recruitment log.

Subject numbers that are assigned by the IWRS will consist of an 8-digit string (a 3-digit trial center identifier and a 5-digit subject identifier connected by “-”). For example, Subject 001-00001 is the first subject enrolled in center number 1. Subject numbers should not be reassigned for any reason.

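### In South Korea, Mexico and Thailand the open-label group is assigned before the baseline blood draw that decides whether the child stays, an avoidable unblinded exclusion after randomisation

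*Protocol*

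**What the plan says.** Protocol Section 5.1.4 sets out Visit 1 for South Korea, Mexico and Thailand in numbered steps. Step 7 is "Connect to the Interactive Web Response System (IWRS) for subject identification number and randomization". Step 8 is the first blood sample and step 9 is vaccination. The title of the visit and the Table of Study Procedures list these items in the same order.

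Step 8 also covers a failed draw. If reasonable attempts, judged by local rules and practice, do not succeed, "then Visit 1 can be rescheduled to a later date at which point informed consent and inclusion/exclusion criteria must be re-validated". Failing that, "If the first blood draw cannot be obtained, the subject will be withdrawn from the study without being vaccinated". Section 5.2.9 adds: "Withdrawn subjects will not be replaced".

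On knowledge of the group, Section 6.5 states: "The IWRS will then provide the group assignment and have the site staff confirm it". Section 6.4 states: "This trial is open label; therefore, there is no need for code-breaking procedures". Only the serology laboratory is blinded.

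In the Russian Federation the order is reversed. At Visit 0, step 8 is "Connect to the Interactive Web Response System (IWRS) for allocation of subject identification number" and step 9 is the blood draw. Randomisation waits until Visit 1, step 4, where staff connect "for subject randomization and obtain group of vaccination allocated". A note in the same section keeps this order when both visits fall on one day.

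**The concern.** A condition for staying in the trial is applied after allocation, by people who know the allocation. Two decisions are exposed: when site staff conclude that further attempts are not reasonable, and what happens at a rescheduled visit, where consent and eligibility must be confirmed again. If either depends on the group, even slightly, the children who remain are no longer a purely random split.

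The location matters. Under Protocol Section 6.5, Group 8 (MenACYW alone, Russian Federation) is filled by age and is not randomised against Group 7. South Korea, Mexico and Thailand are therefore the only countries where MenACYW alone is randomised against concomitant use. The analyses are descriptive, but Protocol Section 1.4 and the SAP Introduction give the purpose as showing that the profiles with and without concomitant vaccines are comparable. That reading depends on groups that differ only by vaccine.

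**Working it through.** The plan states no figure on this point, so there is none to reproduce. The check follows one child through the definitions and then sizes the effect under stated assumptions.

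**1. Tracing a child randomised at step 7 whose draw is never obtained**

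- Full Analysis Set (Protocol 12.2.1, SAP 5.2.1): requires at least one dose and a valid post-vaccination result. Not included.
- Per-Protocol Analysis Set (Protocol 12.2.3, SAP 5.2.2): a subset of the Full Analysis Set. Not included.
- Safety Analysis Set (Protocol 12.2.2, SAP 5.2.3): requires at least one dose. Not included.
- No all-randomised set is defined (Protocol 12.2, SAP 5.2).
- The five reasons for early termination in Protocol 5.2.11 do not name a failed baseline draw, so the cause of the loss may not be identifiable afterwards.

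**2. Children and sites under this order** (Synopsis, Planned Sample Size and Trial Centers)

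- Children: South Korea 200 + Mexico 400 + Thailand 200 = 800. The twelve planned groups sum to 1200, and 1200 − 400 in the Russian Federation = 800.
- Sites: 13 + 3 + 2 = 18 of 29.

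**3. Number lost.** The documents give no rate of final draw failure, so f is an assumption. Lost children = 800 × f.

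| Assumed f | Lost of 800 | Lost in a 200 / 100 / 100 split |
|---|---|---|
| 1% | 8 | 2 / 1 / 1 |
| 2% | 16 | 4 / 2 / 2 |
| 5% | 40 | 10 / 5 / 5 |
| 10% | 80 | 20 / 10 / 10 |

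**4. Possible bias in a between-group difference in response percentage.** Let fA and fB be the loss fractions in two groups, and d the amount by which lost children would have responded less often than retained children, taken as equal in both groups. The observed percentage in a group exceeds its full-group value by f × d, so the difference shifts by (fA − fB) × d.

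- fA = fB: shift = 0 for any d.
- 2% v 1%, d = 10 points: 0.01 × 10 = 0.1 points.
- 5% v 1%, d = 30 points: 0.04 × 30 = 1.2 points.
- 10% v 2%, d = 30 points: 0.08 × 30 = 2.4 points.

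Both the imbalance and d are assumptions; the documents give neither.

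**5. Scale for comparison.** At an assumed 90% response in both groups, the normal-approximation 95% half-width of a difference is 1.96 × √(0.09/100 + 0.09/50) = 10.2 points for 100 v 50, and 1.96 × √(0.09/200 + 0.09/100) = 7.2 points for 200 v 100. The whole assumed range of shifts lies well inside these.

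**The case against.** The strongest reply is that little turns on this. No hypothesis is tested, and the SAP plans single-group percentages and geometric means with single-group intervals, so no decision rule can flip. A child without a baseline sample, a vaccine or a later sample has nothing to analyse, and even an all-randomised set could not recover an outcome. A link between a difficult blood draw and antibody response is not documented. The toddler data in Protocol Section 1.2.2.4 (hSBA titre of at least 1:8 in 97.8% to 100% after MenACYW) leave little room for large shifts. All of this stands, and it keeps the point small. It does not give a reason for the order: an exclusion after randomisation that can be avoided at almost no cost is still better avoided.

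Several stronger readings are tempting, and the documents do not support them.

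- A reader might infer that the parent knows the group at step 7 and returns, or not, accordingly. A motive can be imagined, since exclusion criterion 2 bars other planned vaccines except influenza until Visit 2, which defers the routine vaccine in the MenACYW-alone groups. But no section says the parent is told at that step. Section 6.5 gives the group to site staff and leaves detail to the Operating Guidelines, which are not available here.
- A reader might infer that staff are free to try as hard as they like. The text ties reasonable attempts to local regulations and practice, which limits discretion without removing it.
- A reader might take the 1.2 points as an estimate. It rests on an assumed failure rate, a fivefold imbalance and a 30-point response gap, none of them in the documents.
- A reader might infer that planned group sizes are eroded below need. The sample-size text is not available, so any allowance for attrition cannot be seen, and the South Korean and Thai sizes are called approximate.
- A reader might take the Russian order as a deliberate safeguard. It accompanies a screening visit required for local safety tests, and its text also says that a child with a failed draw is withdrawn. It shows that the order is feasible, not that it was chosen to protect allocation.

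**Conclusion.** The point holds as a matter of procedure. In three of the four countries, covering 800 of 1200 planned children, the group is assigned and visible to staff before a step that can remove the child, and a child removed there is in no analysis set. This is an avoidable, unblinded exclusion after randomisation.

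Confidence is high about the order of steps and the analysis-set definitions. It is low about any numerical effect. Rescheduling rescues some children, so only those whose sample is never obtained, or who lapse or fail re-validation at the rescheduled visit, are lost. Under the assumed rates the loss is 8 to 40 children at 1% to 5%, and the shift in a difference is about 0.1 to 2.4 points if failure is unequal and lost children respond less often. If failure is unrelated to group, expected bias is zero and only some precision is lost. The effect is probably small; this is a cheap improvement rather than a threat to the trial's conclusions.

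**What to change.** - In Protocol Section 5.1.4 (Visit 1, South Korea, Mexico and Thailand), split step 7. The web system issues the subject number, the baseline sample is obtained, and the group is released only after that succeeds. Match the Table of Study Procedures, where randomisation and number allocation now share one row ahead of the draw, and SAP Table 3.1, which repeats it.
- Reword the failed-draw text in Section 5.1.4 (Visit 0 step 9 and Visit 1 step 8) and Section 5.2.9, so that a child whose draw fails before randomisation is a screening failure and not a withdrawal. Changing the order alone does not achieve this, because the Russian text also says withdrawn.
- For children already randomised, have the SAP's disposition table show those randomised but not vaccinated, by group and reason, with failed baseline draw as a separate reason. SAP Section 4.4.1.4.6 mentions the table but does not ask for this.

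The cost is protocol wording and a second web-system transaction at the same visit; the system already separates the two steps for the Russian sites. The tube label needs only the subject number (Section 7.1.1), so sampling does not depend on the group. One small downside is that the sampling limb is chosen before the group is known, but Section 7.1.1 asks for the limb opposite the vaccination only where feasible.

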***SAEs and AEs That Are Related to Vaccination or That Led to Discontinuation:***

At any time during the study, a subject who experiences an SAE or an AE must be followed if *either* of the following is true:

The SAE or AE is considered by the Investigator to be related to vaccination, and is not resolved by the end of the subject's participation in the trial

The subject has been discontinued from the trial because of the SAE or AE

Any such subject must be followed until the condition resolves, becomes stable, or becomes chronic.

### 5.1.5 Planned Trial Calendar

The following dates are approximate. The actual dates may differ as, for example, the trial will not start until all the appropriate regulatory and ethical approvals have been obtained.

Planned subject participation – FVFS (first visit, first subject) to  
LVLS (Last visit, last subject): 07 November 2016 to 11 June 2018

Planned inclusion period - FVFS to  
FVLS (first visit, last subject): 07 November 2016 to 30 April 2018

Planned vaccination period: 07 November 2016 to 30 April 2018

Planned end of trial (last assay results available): 04 September 2018

Planned date of final clinical study report: 31 January 2019

The date that the last assay results are available is considered as the end of the study.

### 5.1.6 Early Safety Data Review

This trial will not include an early safety data review (i.e., no early safety review[s] of preliminary safety data occurring at pre-determined milestones defined in the protocol, with pause in enrollment). However, it may be interrupted at any time if new data about the investigational product become available, and/or on advice of the Sponsor, the IECs / IRBs, or the governing regulatory authorities in the country where the trial is taking place.

If the trial is prematurely terminated or suspended, the Sponsor will promptly inform the Investigators, the IECs / IRBs, and the regulatory authorities of the reason for the termination or suspension. If the trial is prematurely terminated for any reason, the Investigator will promptly inform the subject's parents / guardian and should assure appropriate therapy and follow-up.

